5 PLANNED ANALYSES

5.1 Changes from planned analyses in the Protocol

There are no changes from planned Analyses in the Protocol.

5.2 Interim Analyses

After Stage 1 data completed, Stage 1 analyses will be performed.

5.3 Final Analyses and Reporting

All final planned analyses per protocol and this SAP will be performed only after database lock.

6 ANALYSIS POPULATIONS

All data will be presented in listings for the Enrolled population. A subject will be considered enrolled when the subject has been consented, screened, and all eligibility criteria have been confirmed in the electronic case report form (eCRF).

6.1 Pharmacokinetic Population

6.1.1 Pharmacokinetic Population for Stage 1

The Pharmacokinetic (PK) Population will consist of all subjects who received ENT-01 and for whom there are adequate samples collected to provide analyzable PK parameters.

Any subject who violates the protocol in a way which might influence the plasma concentration by time profiles will be excluded from the PK population.

6.1.2 Pharmacokinetic Population for Stage 2

Seven subjects from the ENT-01 group and three subjects from the placebo group will be selected for the Pharmacokinetic (PK) Population.

Any subject who violates the protocol in a way which might influence the plasma concentration by time profiles will be excluded from the PK population.

6.2 Safety Population

For each stage, safety Population will consist of all subjects who receive at least one dose of ENT-01 during that stage.

6.3 Full Analysis Set

For each stage, full Analysis Set (FAS) includes subjects who are treated with ENT-01 in the treatment period and have the stool diary assessments both at baseline and at least one post baseline.

6.4 Randomized population

For Stage 2, randomized population included all subjects who are randomized and receive at least one dose of blinded treatment under the protocol dated 27 July, 2017.

7 STATISTICAL CONSIDERATIONS

All analyses described in this plan are considered a priori analyses in that they have been defined prior to locking the database. All other analyses, if any, designed subsequently to locking the database, will be considered post hoc analyses and will be described as exploratory analyses in the Clinical Study Report.

All summaries and statistical analysis will be performed by SAS® Version 9.3 or later for each stage separately.

7.1 General Statistical Procedures

Frequency distributions for categorical variables will be provided as counts of subjects and percentages. Percentages will be based on the number of subjects with a non-missing parameter unless missing category is presented. Percentages will be reported to one decimal place.

The descriptive statistics for continuous variables will be number of subjects, arithmetic mean, standard deviation (SD), median, quartiles (Q1, Q3), minimum and maximum. Arithmetic mean, median, Q1, and Q3 will be reported to 1 more decimal place than the raw data, while the SD will be reported to two more decimal places than the raw data.

In addition to the above descriptive statistics, the coefficient of variation (CV%) will also be used for the summaries of drug concentration data and pharmacokinetic parameter values. The geometric means will be calculated for AUC and Cmax values.

All data listings that contain an evaluation date will also contain a relative study day.

Missing values will not be imputed.

7.2 Enrollment and Disposition

7.2.1 Subjects Enrollment

Subject enrollment will be summarized for each analysis population separately for each stage. The number of subjects in each analysis population will be presented.

Enrollment information will be provided in a data listing.

7.2.2 Subject Disposition

7.2.3 Subject Disposition for Stage 1

Subject disposition will be summarized for each dose of ENT-01 and overall. Number and percentage of subjects who complete each dose, number and percentage of subjects who discontinued from the study early by primary reasons will be presented. The denominators for calculating the percentages will be based on number of subjects enrolled.

Discontinued subjects will be provided in a data listing.

7.2.4 Subject Disposition for Stage 2

Subject disposition will be summarized for each period and for each analysis population. Number and percentage of subjects who complete the full protocol, number and percentage of subjects who discontinued from the study early by primary reasons will be presented. The denominators for calculating the percentages will be based on number of subjects in the analysis population.

Discontinued subjects will be provided in a data listing.

7.3 Protocol Deviations

Important or significant protocol deviations (PD) will be assessed by sponsor personnel following Protocol Deviation Guideline outlined in Clinical Management Plan.

- A PD is classified as important if there is the potential to impact the completeness, accuracy, and/or reliability of the study data, or affect a subject's rights, safety, or well-being.
- An important PD is classified as significant if it is confirmed to adversely impact the completeness, accuracy, and/or reliability of the study data, or affect a subject's rights, safety, or well-being.

All PDs will be identified and finalized prior to database lock.

All protocol deviations will be listed. Protocol deviations will be presented in summary tables separately for each stage for the Safety population.

7.4 Demographics and Baseline Characteristics

7.4.1 Demographics and Baseline Characteristics

Demographic and baseline characteristics will be summarized overall for each analysis population as applicable.

The demographic data are:

- Age
- Sex
- Race
- If female, childbearing potential (Yes/No)
- Ethnicity
- Height (cm)

- Baseline Weight (kg)
- BMI (Body mass index, kg/m², calculated as Weight (kg) / Height (m)²)

Conversions for height and weight are as follows:

$$\text{Height (cm)} = \text{Height (inches)} \times 2.54$$

$$\text{Weight (kg)} = \text{Weight (lb)} \times 0.4536$$

The demographic data will be listed.

7.4.2 Baseline Disease Characteristics

Age at diagnosis of Parkinson's disease, years with Parkinson's disease, years of constipations, Hoehn and Yahr stage, and constipation severity – CSBM will be summarized as appropriate for each analysis population.

Baseline disease characteristics will be provided in a listing.

7.4.3 Medical History

In Stage 2, general medical history will be collected. The medical history will be coded using the current version of the Medical Dictionary for Regulatory Activities (MedDRA). The frequency count and percentage of patients experiencing any medical conditions will be tabulated by MedDRA system organ class (SOC) and preferred term (PT) for the Safety and Randomized population. The denominators for calculating the percentages will be based on number of patients in the analysis population.

A data listing of medical history will be provided.

7.5 Prior and Concomitant Medications

All medications as documented by the investigator will be coded using the World Health Organization (WHO) Drug Dictionary. The count and percentage of subjects who take prior/concomitant medications will be provided using therapeutic class and WHO Drug preferred name. The denominators for calculating percentages will be based on the number of subjects overall in the Safety population. For the summary tables, if a subjects took a prior or concomitant medication more than once, the subject would be counted only once for each therapeutic class and preferred name.

Prior medications are defined as medications taken prior to the first dose of study drug (ENT-01). Concomitant medications are defined as medications taken on or after the first dose study drug. Prior and concomitant medications will be summarized overall for the safety population.

For Randomized population, concomitant medications will be summarized by treatment.

All prior and concomitant medications, including ancillary medication will be listed.

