therapeutic effect. Should there be more than 1 patient with AE grade 4 or 5 that is at least possibly

related to ENT-01 for doses less than 200 mg, the study will be put on an immediate safety hold

until an emergency DSMB meeting can be held to evaluate the study for possible discontinuation.

Dose-finding: Beyond the safety and tolerability, this Period will allow us to determine the dose

which is safe and tolerable in all 10 patients (STD) and which has a pro-kinetic effect in at least

some patients (STDE: Safe and Tolerable dose in all and pro-kinetic Effect in at least some). We

will start Period 3 with the STDE.

PERIOD 2.2 (Stage 1): Washout

Duration: 2 weeks

Patients will be observed off study drug and adverse events will be recorded. They will

continue to keep a daily diary throughout the period. They will continue to wear the I-Button for

five 24 hour periods between Days 1 and 5. During the second week, they will be restarted on all

original medications but will continue their diaries until the termination of the study. They will be

seen prior to study termination and BDI, MMSE, Trail making A and B, NMSQ, UM-PDHQ, PFS-

16, RBDQ, PDSS, PAQ-SYM and PAC-QOL will be administered.

Visit 2: Day 14

Patients will be reviewed prior to discharge and any adverse events noted.

DSMB review of Stage 1: The DSMB will determine whether to proceed to Stage 2.

PERIOD 3.1 (Stage 2a)

Run-in period for Cohort 2 (n=40)

Duration: 2 weeks

Conducted at home.

28

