Patients will be taken off study drug. They will continue to keep a daily diary throughout the period. They will be contacted by phone daily during Week One to check diaries and laxative use. During the first week of the wash-out period they will only use rescue medication as needed. During the second week, they will be restarted on all original medications including laxatives but will continue their diaries until the termination of the study. They will continue to wear the I-Button for the first 5 days of this period. During the last visit, the UPDRS, BDI, Trail-Making A and B, MMSE, PFS-16, NMSQ, UM-PDHQ, RBDQ, PDSS, PAC-SYM and PAC-QOL will be administered

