APPENDIX 2: SCHEDULES OF EVENTS

STAGE 1

Period	Ru Ser	1 n-In ntinel wks	2.1 Single Dose 3-8 wks	2.2 Wash-Out 2 wks
	D1	D14	D1	
Consent	X			
Demographics	X			
Inclusion/exclusion	X	x		
Medical history	X			
Physical exam	X		X	x
Vital signs ¹	X		X	x
Rome-IV	X			
Blood chemistry	X		х	х
Hematology	X			
Urinalysis	X			х
Fecal occult blood	X		х	х
EKG	X		х	х
Pregnancy test	X			
Monitoring			х	х
Discontinue medications	X			
Re-start medications				х
Diary entries	X	x	х	х
UPDRS	X		X^4	x ²
I-Button ³	X	х	X	
PAC-QOL	X	х	X ⁴	x ²
PAC_SYM	X	X	X ⁴	x ²
RBDQ	X		X ⁴	x ²
NMSQ	х		X ⁴	x ²
PFS-16	х		X ⁴	x ²
UM-PDHQ	х		X ⁴	x ²

BDI	X		X ⁴	\mathbf{x}^2
Trail-making A and B	X		X ⁴	x ²
MMSE	X		X ⁴	\mathbf{x}^2
Adverse events		Х	X	х
PK samples			X ⁵	
Schedule visit days	X			
Administer ENT Dose			X	
Record Medications	X	Х	X	x
Daily phone calls to on non-visit days		Х	X	х

¹Vital signs taken before dose and 2 hours after dose

²End of period 2

³I-Button placed days 9 of run-in periods and worn continuously through day 5 of wash-out periods.

⁴Surveys taken at last dosing visit

⁵PK samples taken pre-dose and 1, 2, 4, 8 and 24 hours post-dose

STAGE 2

		Period 3.1 Run-In					Period 3.2 Multiple Dose		Period 4 domized Treat	ment	Period 5 Wash-Out	
	Day 1 Visit 1	Days 2-7, 9- 10, 12-13 Calls	Day 8 Call	Day 11 Visit 2	Day 14 Call	Days 1-13, 15-16 Calls	Day 14 Call	Day 1 Visit 3 ⁶	Days 2-5 Calls	Day 6 Visit 4	Days 1-7 Calls	Day 14 Visit 5
Informed Consent	X											
Inclusion/Exclusion Criteria	X											
Demographics/Medical History	X											
Prior and Con Meds	X											
Complete Physical Exam	X											X
Height	X											
Weight	X			X				X		X		X
Vital Signs ¹	X			X				X		X		X
ECG	X							X				X
Local Labs - Chemistry, Hematology	X							X		X		X
Local Labs - Urinalysis, Serum Pregnancy	X											
Fecal Occult Blood	X							X				X
Randomization								X				
Study Drug Dispense, Accountability, or Collection				Х				X		X		
Reminder to Begin Taking Study Drug the Next Morning					X							
Instructions to Discontinue Laxatives and other BM Medications	X											
Instructions to Resume Laxatives and other BM medications												X
Stool and Sleep eDiary Instruction/Review	X	X	X	X	X	X	X	X	X	X	X	X
AE Review		X	X	X	X	X	X	X	X	X	X	X
Rome IV questionnaire	X		X									
UPDRS	X							X				X
PAC-QOL and PAC-SYM	X				X		X	X		X		X
Questionnaires - BDI, NMSQ, PFS-16, UM- PDHQ, MMSE, Trail-Making A and B, RBDQ and PDSS	X							X		X		Х

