8.8 Handling of Partial Dates for Medications

A medication with a completely missing start date will be considered a prior medication. A medication with a completely missing stop date will be considered to be ongoing.

When determining prior or concomitant medications, partial start dates of prior and concomitant medications will be assumed to be the earliest possible date consistent with the partial date. Partial stop dates of prior and concomitant medications will be assumed to be the latest possible date consistent with the partial date.

9 Changes to the Planned Analyses in the Protocol(s)

Because protocol amendment dated 02 February 2018 removed randomization portion during the trial, there will not be enough samples size to do the following analysis specified in the original protocol dated dated 27 July 2017. Therefore, the following analysis will not be performed for CSR.

- A secondary analysis will compare the proportions of subjects who are deemed a success at the end of the randomized fixed-dose period between those randomized to the ENT-01 arm and those randomized to the placebo arm. Subjects to be included in this analysis will only be those who have been randomized. If the number of subjects for this analysis is between 20 and 30, a Fisher's exact test will be used to compare the proportions of subjects who are deemed a success at the end of randomization period between the two randomized arms.

The protocol also proposed the following analysis as below:

- Another secondary analysis will compare the proportions of subjects who are a success (compared to baseline) between the end of the first week of the washout period (period 5) and the end of the fixed-dose period (period 4). This analysis will consist only of those subjects with assessments at baseline (end of run-in period, Period 3.1), the end of Period 4, and the end of Period 5. If the number of subjects for this analysis is between 17 and 20 subjects, this analysis will be done using an exact sign test of equality of paired proportions.

In this analysis, using the end of the first week of washout is not consistent with the time frame for other PD parameters (note: other PD parameters' are all evaluated using two weeks of washout data, i.e., the end of 2 weeks). Therefore, it was determined we would not do this analysis for CSR.

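### Concomitant medication has a start date but no end date, so drugs taken only in washout, and by arm only in open-label dosing, are tabulated as taken with study treatment (minor)

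*SAP*

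**What the plan says.** SAP 7.5 splits medications at the first ENT-01 dose. Those taken before it are prior. For the rest: "Concomitant medications are defined as medications taken on or after the first dose study drug". Each subject is counted once per therapeutic class and preferred name, and all medications are also listed. The section then adds: "For Randomized population, concomitant medications will be summarized by treatment". SAP 6.4 defines that group: "randomized population included all subjects who are randomized and receive at least one dose of blinded treatment", under the 27 July 2017 protocol only.

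SAP 8.8 deals with partial and missing dates, for example "A medication with a completely missing stop date will be considered to be ongoing". It sets no end to the concomitant window.

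The protocol (section 3.1) restarts withdrawn drugs after dosing. In Stage 1, Period 2.2, patients go back in the second week to all "original medications but will continue their diaries until the termination of the study". In Stage 2, Period 5: "During the second week, they will be restarted on all original medications including laxatives". Protocol 4.6 reinstates proton pump inhibitors in washout in both stages. Note 6 to SAP Table 4 (the 2018 schedule) has laxatives, bulking agents, softeners, proton pump inhibitors and antacids resumed after the first washout week.

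**The concern.** A concomitant table should show what patients took while on study drug. An open-ended window often does little harm, because most drugs taken after treatment were also taken during it. This trial differs, because it takes patients off a set of drugs for dosing and puts them back on afterwards. The definition therefore mislabels the very drugs of interest: a proton pump inhibitor or laxative that was off during dosing and restarted in washout looks the same in the table as one taken with ENT-01.

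The by-arm table has a second problem. In Stage 2 the first ENT-01 dose falls in Period 3.2, before randomization, when every patient is on active drug. Without a new start date, a drug used only then by a patient later assigned to placebo is shown under placebo.

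The primary analysis compares on-drug success with a fixed 0.10 and has no concurrent control, so readers will want to know whether withdrawn drugs stayed off during dosing. As defined, this table does not show that.

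**Working it through.** The plan gives no figure to reproduce. The check is whether any rule closes the window, how long it then runs, and what happens to typical entries.

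**1. Does another rule close the window?** SAP 6.4, 7.5, 8.1 and 8.8 do not. Other SAP sections do set limits:
- SAP 7.8.1 restricts by-arm adverse events to the randomization period and gives washout its own category in the overall Stage 2 table.
- SAP 7.8.2, 7.8.3, 7.8.4 and 7.8.6 treat the randomization period separately.
- SAP 4.4 places the start of Stage 2 washout 24 hours from the last dose.

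Section 7.5 uses none of these limits.

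**2. Length of the window, Stage 2, 27 July 2017 protocol.** Inputs from protocol 3.1: Period 3.2 lasts at least 5 days (5 to 7 consecutive days on the pro-kinetic dose, if the first level works) and at most 19 (stated range 17 to 19). Period 4 lasts 6 days and washout 14.

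Window = Period 3.2 + Period 4 + washout
- Shortest: 5 + 6 + 14 = 25 days
- Longest: 19 + 6 + 14 = 39 days
- With the 17-day limit in the section 3 design table: 17 + 6 + 14 = 37 days

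Ending the window at the last dose leaves 5 + 6 = 11 to 19 + 6 = 25 days overall. Limiting the by-arm table to blinded dosing leaves 6 days.

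**3. Where typical entries land.**

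| Recorded use | SAP 7.5 as written | With a bounded window |
|---|---|---|
| Withdrawn at run-in, restarted in washout week 2 | Prior and concomitant | Prior and post-treatment |
| Used only in Period 3.2, patient later on placebo | Concomitant; placebo column | Concomitant overall; not in the by-arm table |
| Started in washout after Period 4 | Concomitant; credited to the arm | Post-treatment |
| Stable drug continued throughout | Concomitant; credited to the arm | Same |
| Rescue suppository in Period 4 | Concomitant; credited to the arm | Same |

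The first three rows are misplaced and the last two are not. Because subjects are counted once per class and name, the table cannot separate the first row from true use on drug.

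**4. Is washout use recorded?** The Stage 1 schedule marks medication recording in washout. SAP Table 4 marks concomitant medications at contacts through the Day 14 washout visit. The 27 July 2017 Stage 2 schedule marks "Prior and Con Meds" at Visit 1 only. The overall-table problem is therefore clear for Stage 1 and the 2018 schedule. How much reaches the by-arm table depends on what sites recorded beyond that schedule.

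**The case against.** The case against is mostly about size, and much of it stands.

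- **No inference depends on these tables.** SAP 7.7 plans no formal comparison of the arms on pharmacodynamic variables, and SAP 9 drops the randomized success comparison. The stool endpoint takes rescue use from the diary. This stands.
- **Prohibited use can be seen elsewhere.** A reader might infer that this table is the only summary of the withdrawn drugs. It is not. SAP 7.3 tabulates and lists protocol deviations, and SAP 7.5 lists every medication. With 10 and 40 planned subjects, use on drug can be separated from later use by hand where dates are recorded. SAP 7.3 does not, however, promise a breakdown by drug or period.
- **The size of the error is unknown.** Since eligibility requires regular laxative use and laxatives are restarted, a reader might infer that nearly every completer will show a false concomitant laxative. The documents do not support that. The 2017 Stage 2 schedule marks no medication recording after Visit 1, nothing says diary laxatives enter the coded medication data, and rescue during dosing is permitted and truly concomitant. Nor does 6 days out of 25 to 39 measure the error, because the table counts subjects once per drug, not days.
- **Missing stop dates.** A reader might infer that SAP 8.8 carries drugs withdrawn at run-in into dosing as ongoing. Nothing shows that such dates will be missing, and protocol 12.15 asks for an explanation of all missing data.
- **Follow-up medications matter for safety.** Protocol 9.13 collects adverse events to 30 days after the last dose. This is a reason to keep later medications in view under their own label. It does not justify calling them concomitant.

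**Conclusion.** The point holds as a minor one. SAP 7.5 states a rule that, read literally, places drugs taken only after ENT-01 in the concomitant table for Stage 1 and for Stage 2 under the 2018 schedule. It also credits recorded open-label and washout use to an arm in the Randomized population. This is more than missing detail, because the stated rule gives a wrong label.

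The effect is confined to descriptive tables. The primary test is unaffected, and the listings keep the recorded dates. No count of misplaced entries can be given. The conclusion assumes that the programmer applies the definition as written and that washout medications are recorded where the schedules say so. The by-arm part concerns only subjects randomized under the 27 July 2017 protocol and depends on what was recorded for them after Visit 1. New collection in that superseded Period 4 is not a sensible request, since the 2018 amendment removed randomization.

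**What to change.** Amend SAP 7.5 before database lock:

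1. Concomitant: any use from the first ENT-01 dose in the stage to 24 hours after the last study-drug dose. This is the boundary SAP 4.4 already uses for Stage 2 diaries. Another stated end would also serve; what matters is that one is fixed.
2. Post-treatment: drugs started or restarted after that point, shown in a separate washout category as SAP 7.8.1 does for adverse events.
3. Randomized population: count only use between the first and last blinded dose, matching the limit in SAP 7.8.1.

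The cost is a few lines of SAP text and one derivation on dates already held. No new data collection and no change to any test is needed.

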7.6 Analysis of Pharmacokinetic Data

7.6.1 Summary of Pharmacokinetic Concentration Data for Stage 1

All plasma concentration data will be summarized based on the PK population by timepoint (pre-dose, 1, 2, 4, 8 and 24 hours post-dose) and dose level in terms of n, mean, SD, CV%, median, minimum, maximum, geometric mean, and geometric CV%.

Individual plasma concentration will be listed by timepoint and dosage. The concentration will be listed to the same degree of accuracy as supplied by the analytical laboratory and PK group. As well, the units of concentration will be presented as they are received from the bioanalytical laboratory and PK group.

Individual concentration and mean plasma concentration will be displayed graphically.

Summary of Pharmacokinetic Concentration Data for Stage 2

Individual plasma concentration will be listed by timepoint for the PK population. The concentration will be listed to the same degree of accuracy as supplied by the analytical laboratory and PK group. As well, the units of concentration will be presented as they are received from the bioanalytical laboratory and PK group.

Individual concentration will be displayed graphically using actual sampling times.

